# **2.2 RATIONALE**

Providers routinely prescribe alpha antagonists and/or anticholinergics to patients in order to relax the bladder and minimize the discomfort. Numerous studies have investigated the beneficial effect of alpha antagonists for ureteral stent-related discomfort. Tamsulosin is a selective  $\alpha_{1a}$ -blocker that antagonizes  $\alpha_1$  mediated contraction of prostate, bladder and proximal urethral smooth muscle. Owing to this mechanism, it reduces urethral and bladder outlet resistance and decreases urinary reflux, ureteric motility and bladder hyperactivity, all of which work to alleviate stent-related discomfort. Similarly, many studies have evaluated the utility of anticholinergics in treating stent discomfort since many of the stent-related symptoms are similar to overactive bladder symptoms caused by muscarinic receptor mediated involuntary bladder contractions. Hyoscyamine is a prescription drug that became available before 1938 and is considered a 'Grandfather Drug.' Hyoscyamine is one of the least expensive anticholinergics on the market, and furthermore, it has more favorable pharmacokinetics compared to other anticholinergics that are typically prescribed for stent-related discomfort. Oxybutynin, for example, has an onset of action of 30 minutes to 1 hour with time to peak effect of 3 to 6 hours, compared to Hyoscyamine which has an onset of action of 2-3 minutes with time to peak effect of 30 minutes to 1 hour. Since stent-related discomfort can be aggravated with activity and typically presents in a waxing and waning fashion, the rapid acting therapeutic effects of hyoscyamine may provide tremendous relief for patients with indwelling stents. A review of literature in PubMed did not yield any studies evaluating the efficacy of hyoscyamine in the treatment of stent-related discomfort. Since we routinely use hyoscyamine to treat patients with ureteral stent discomfort, it would be interesting to know how effective hyoscyamine is when used in this setting. Given the well-published data on tamsulosin, we would like to conduct a formal study comparing the efficacy of hyoscyamine to tamsulosin for treating symptoms associated with ureteral stents as assessed by a validated questionnaire, the Ureteral Stent Symptom Questionnaire, and provide the first research-based evidence regarding the efficacy of hyoscyamine for the treatment of stent-related discomfort.

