# **5.3 STUDY PROCEDURES**

To assess ureteral stent symptoms, we will be conducting the Ureteric Stent Symptoms Questionnaire (USSQ). The USSQ was created by Joshi et al as an instrument to measure stentrelated morbidity. The USSQ has been validated as a reliable instrument to measure the impact of ureteral stents. This validated questionnaire has been used in many previous studies regarding stent pain. In our study, the USSQ will be conducted prior to stent placement, on POD1, POD7 (or just prior to the time of stent removal if the removal occurs prior to day 7), and POD30. Basic demographic information, stent duration, stent size, stone location/size and obstructing vs. non-obstructing (if applicable), post stent insertion complications, drug diary information and questionnaire responses will be entered into a REDCap database for storage and analysis. The stent diameter will be 6Fr for all patients in the study. The appropriate stent length will be assigned to the patient based on cross sectional imaging. If cross sectional imaging is not available then stent length with be measured using a open-ended catheter to measure ureteral length. A small portion of these patients will be seen in the emergency department or while they are having an acute pain episode, so we expect that some of the pre-stenting questionnaires may not provide an accurate baseline for symptoms in these patients, hence the POD30 questionnaire will be obtained.

After informed consent is obtained, the patient will be prospectively randomized to either treatment arm in an open-label fashion using REDCap's randomization function to determine which therapy they will receive after stent placement. In the event that a patient does not find relief with their particular treatment arm, they will be permitted to receive additional narcotics or Pyridium. Should the patient continue to have unrelieved symptoms, treatment crossover is allowed since the study is designed in an intent-to-treat fashion.

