The first arm is hyoscyamine 0.125 mg tab sublingual every 4 hours as needed for discomfort, and the second arm is tamsulosin 0.4mg tab orally daily. Both dosing regimens are standard prescription orders. Both medications are routinely used in our practice, so patients are not being exposed to new safety risks compared to non-study patients. Risks are reasonable, as the medications used in this study are already commonly used in our daily practice. Patients will be given contact numbers for the Urology Department should they have any adverse side effects or concerns. Hyoscyamine is an anticholinergic and can cause side effects including constipation, dry mouth, drowsiness, headache, or lightheadedness. Tamsulosin is an alpha blocker and can

cause side effects including dizziness, fatigue, nasal congestion, syncope and retrograde ejaculation. Patients who have taken alpha blockers are at risk for intraoperative floppy iris syndrome if they are going a cataracts surgery in the near future. Patients will be advised to immediately stop the medicine and seek medical care if they develop the rare but severe reactions of skin rash, swelling, confusion, irregular or fast heartbeat, eye pain, or hallucinations. As part of the standard treatment pathway for post-stent insertion, patients are also sent home with a narcotic pain medication to help with pain and discomfort. Our pathway is to prescribe all patients with 10 tabs of Norco 5/325 1-2 tabs po q6H PRN unless there are contraindications or allergies to this specific narcotic, in which case they are prescribed an alternative narcotic with Percocet 5/325 1-2 tabs po q6H PRN. Patients will be given a drug diary to document their usage of the study medications for stent discomfort, including their narcotic usage, so that this information can be tracked as well. Patients will stop drug diary at time of stent removal.

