# 5.4 STUDY DESIGN AND SAMPLE SIZE

Total sample size: 100

The study will be conducted as a randomized comparative effectiveness trial with two arms. Subjects will be randomized to one of two treatments WITH either hyoscyamine or tamsulosin. Our hypothesis is that the hyoscyamine is at least as effective as tamsulosin in treating lower urinary tract symptoms. Symptoms will be quantified using the Urinary Symptom Index (USI) of the validated Ureteral Stent Symptom Questionnaire (USSQ). To address the hypothesis, the study will be conducted as a non-inferiority trial, following the hypothesis that hyoscyamine is not inferior to tamsulosin by more than a 15% margin in terms of the USI. The sample size was estimated using the PowerTOST package for the R statistical environment, based on a nominal power of 80% and an alpha-level of .025 for the one-sided t-test. Our null hypothesis is therefore that the mean USI for those treated with tamsulosin is more than 15% greater than those treated with hyoscyamine, so that by rejecting it, we may conclude hyoscyamine is not-inferior to tamsulosin by more than a 15% margin of USI for treating lower urinary tract symptoms. Furthermore, we assume that the coefficient of variation (CV) for the mean Urinary Index Score

will be similar to that in Park, et al.20 The CV in that study for the Urinary Symptom Index at week 2 after stent placement for the tamsulosin group was approximately .25. This is slightly higher, but similar to the CV of .22 for the USI in Maldonado-Avila, et al. which collected data at week 1, and therefore should be slightly conservative.21 Using these assumptions, we estimated that the sample size for each arm would need to be approximately 47, in order to have the desired power.

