# **5.5 DATA ANALYSIS**

The main hypothesis of the non-inferiority of hyoscyamine to tamsulosin for treating lower urinary tract symptoms will be tested using a t-test for non-inferiority of the change in USI between POD1 and POD7 (or day of stent removal if removed before day 7) in each treatment arm. This should be slightly more powerful than the t-test at POD7 alone that we used to estimate the sample size, but there are not enough data available for the distribution at POD1 in order to make a good estimate of the change. The non-inferiority margin will be 15% of the change in USI. The primary analysis will be conducted as intention-to-treat (ITT). That is, subjects will be analyzed as belonging to the arm they were randomized to, irrespective of later crossover or other modifications. This approach is in line with the current statement on Consolidated Standards of Reporting Trials (CONSORT). Descriptive statistics will be used to describe the results from all USSQ domains at each timepoint (i.e. mean and standard deviation, along with confidence intervals for urinary symptom index, pain symptom index, etc.). We will also conduct non-inferiority tests of change in score for ITT with hyoscyamine versus tamsulosin for the other domains spanned by the USSQ, including pain symptom index, general health index, work performance index, and sexual matters between POD1 and POD7, although we may not be wellpowered to detect non-inferiority for these additional domains.

The secondary goal of determining if there are differences in the amount of additional medications need to treat stent-related discomfort between treatment arms will be examined primarily through descriptive statistics. The drug diaries of all subjects will be used to tabulate the kinds and amounts of additional medications used. For each subject, the number of days that additional medications were used will be counted. The proportion of days that additional medications were used will be calculated for each group and 95% confidence intervals will be calculated.

Finally, we will also calculate the informed consent rate, and the discontinuation rate for those patients needing to be removed from the study in each arm.

In all cases, a p-value  $\leq$  .05 will be taken as a statistically significant result.

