# **5.6 SCHEDULE OF EVENTS**

Visits	Enrollment	Stent Placement	POD1	POD2	POD3	POD4	POD5	POD6	POD7 A	POD30
USSQ	Х		Х						Х	Х
Randomization	Х									
Complete Medication Diary		Х	Х	Х	Х	Х	Х	Х	Х	
REDCap Survey			Х						Х	Х
Stop Medication									Х	

Footnotes: A = If stent is removed prior to day seven then USSQ will occur on day of stent removal and diary will be stopped. If stent is removed after day seven then USSQ will occur on day seven but the diary will be stopped on day of stent removal.

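### The primary endpoint measures change from POD1, after randomization and with study drug available, so a between-arm gap already present at POD1 that persists cancels out of the test

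*Combined protocol and SAP*

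**What the plan says.** Section 5.5 states that the main hypothesis will be "tested using a t-test for non-inferiority of the change in USI between POD1 and POD7", with the day of stent removal replacing POD7 if removal is earlier. It adds: "The non-inferiority margin will be 15% of the change in USI". The only reason offered for analysing change is power: "This should be slightly more powerful than the t-test at POD7 alone that we used to estimate the sample size". The same sentence concedes that POD1 data are too sparse to estimate the change well.

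Section 5.4 frames the hypothesis on the score itself: "hyoscyamine is not inferior to tamsulosin by more than a 15% margin in terms of the USI".

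On timing, section 5.3 randomizes after consent "to determine which therapy they will receive after stent placement", and section 5.6 marks randomization at enrollment. The row "Complete Medication Diary" in section 5.6 is marked from the stent placement day, and section 5.3 says the diary records study medication as well as narcotics. Section 5.1 describes the pre-stent USSQ as the baseline measurement, but the primary test does not use it.

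**The concern.** A change score is a clean treatment comparison when its starting value is taken before treatment can act. POD1 does not meet that condition: patients have been randomized, the stent is in, and study drug is available. Part of the treatment effect may already be in the value that is subtracted.

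Two errors follow, in opposite directions. If hyoscyamine controls symptoms worse from the first day and stays worse, the deficit disappears from the contrast. In a non-inferiority trial this is the serious direction. If hyoscyamine works earlier and the arms are equal by POD7, it shows less improvement and is penalized. Early action is one of the protocol's reasons for studying the drug; section 2.2 refers to "Hyoscyamine which has an onset of action of 2-3 minutes with time to peak effect of 30 minutes to 1 hour".

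The stated objective is whether hyoscyamine controls stent symptoms no worse than tamsulosin. The POD1-to-POD7 change can give the same answer for an equal drug and for a uniformly worse one.

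**Working it through.** **Inputs from the plan.** One-sided alpha .025, 80% power, margin 15%, CV .25, about 47 per arm (section 5.4); POD7 alone as the sizing endpoint (section 5.5).

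**Assumptions.** Higher USI is worse; SDs are equal at both visits; POD1-POD7 correlation ρ is .3, .5 or .7 (not given in the documents). All quantities are in units of mean USI. Probabilities are from the noncentral t with 92 df, for which the critical value is about 1.986.

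**1. The plan's sample size.** For a POD7 comparison, SE = .25 × √(2/47) = .0516, and the noncentrality is .15/.0516 = 2.91. Power is 82.1% at 47 per arm and 84.4% at 50. The smallest n for 80% is 45 per arm, close to the plan's 47. Log-scale versions give 38 or 50 per arm depending on how the 15% is expressed, and the exact software call is not stated. With a true POD7 gap equal to the margin, the test passes 2.5% of the time, as it should.

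**2. What the primary test estimates.** Let g1 and g7 be the hyoscyamine-minus-tamsulosin gaps in mean USI at POD1 and POD7. The difference between arms in mean change is g7 − g1. If g1 = g7, this is 0 however large the gap.

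**3. SD of the change.** It is .25 × √(2(1 − ρ)) = .296, .250, .194 for ρ = .3, .5, .7. Relative to the POD7 SD this is 1.18, 1.00, .77. With the same margin in points, change is more powerful than POD7 alone only if ρ exceeds .5.

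**4. Probability of declaring non-inferiority, 47 per arm.** Noncentrality = (margin − (g7 − g1)) / (SD of change × √(2/47)).

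| Truth | Margin | ρ = .3 | ρ = .5 | ρ = .7 |
|---|---|---|---|---|
| Equal, or worse by any constant amount on both days | .03 | 7.0% | 8.3% | 11.2% |
| Equal at POD7, 5% better at POD1 | .03 | 1.1% | 1.0% | 0.7% |
| Equal at POD7, 10% better at POD1 | .03 | 0.10% | 0.05% | 0.01% |
| Equal, or worse by any constant amount on both days | .15 | 68.2% | 82.1% | 96.0% |
| Equal at POD7, 5% better at POD1 | .15 | 36.8% | 48.4% | 69.8% |
| Equal at POD7, 10% better at POD1 | .15 | 12.5% | 15.9% | 23.5% |

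The margin of .03 is section 5.5 as written, 15% of the change, with an assumed tamsulosin change of 20% of mean USI (.15 × .20). For assumed changes of 10% to 50% of mean USI, the first row ranges from 4% to 46%. The margin of .15 applies section 5.4's 15% of USI to the section 5.5 change test.

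For comparison, a POD7 test with margin .15 passes 82.1% of the time for a drug equal at POD7, whatever happened at POD1, and 2.5% for one 15% worse.

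**5. Partial persistence.** With a deficit of .15 at POD1 and .225 at POD7, the contrast sees .225 − .15 = .075. With margin .15 and ρ = .5, the change test passes 30% of the time although the POD7 deficit exceeds the margin.

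**6. Simulation checks.** With 10,000 trials, margin .15 and a constant deficit of .15 or .30, the change test passed 68–69%, 82–83% and 96% of the time; the POD7 test passed about 2.5% and 0%. With 40,000 trials, margin .03 and a constant deficit of .15, the change test passed 7.1%, 8.4% and 11.3%. Setting the margin to 15% of the observed tamsulosin change gave 7.7%, 9.1% and 12.3% (20,000 trials).

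**The case against.** The strongest reply is that the harm needs a POD1 gap, and nothing in the documents shows one. Section 5.3 gives "hyoscyamine 0.125 mg tab sublingual every 4 hours as needed for discomfort", and the time of first dose is not stated. The diary also records narcotics, so a mark on the placement day does not prove that study drug was taken. This stands: the documents support drug available by POD1, not drug taken by every patient. The two harms also need POD1 gaps of opposite sign, so one trial cannot show both. But a primary test should not depend on neither drug having acted before its reference measurement.

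Fast onset is only one of several reasons given in section 2.2, and the comparison there is with oxybutynin, not tamsulosin. This also stands; it makes an early difference plausible without establishing it.

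The 68%/82%/96% figures combine the test of section 5.5 with the margin of section 5.4. That is fair. Under the margin as written, false passes are much rarer, but an equal drug also fails 89–93% of the time at the assumed 20% change. Most of that failure comes from the small margin, which is a separate defect. The inability to separate an equal drug from a uniformly worse one remains under either margin.

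POD1 is the only scheduled early score with the stent in place, and section 5.3 warns that some pre-stent scores may be inaccurate. That makes the choice understandable, although the plan does not give this reason. It bears only on whether to adjust for the pre-stent score; a POD7 comparison of randomized arms needs no baseline.

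The planned descriptive statistics at each timepoint would show a POD1 gap, but they do not enter the decision.

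**Conclusion.** The concern holds and must be fixed. The cancellation is exact for any gap that is the same at POD1 and POD7, and it depends on no assumed figure. Its practical size depends on a POD1 gap and a POD1-POD7 correlation that the documents do not give, so the pass rates above are illustrations under the stated assumptions. The power argument for using change is unsupported: it requires a correlation above .5 with the same margin in points, whereas section 5.5 also changes the margin and admits that the POD1 data are lacking.

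**What to change.** In section 5.5, make the primary endpoint the USI at POD7, or just before stent removal if that is earlier. Replace the margin of 15% of the change with 15% of USI, as in section 5.4, and state which mean the 15% refers to and whether it is fixed in advance or estimated.

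A t-test on POD7 USI removes the defect. ANCOVA with the pre-stent USI as covariate is preferable, but its gain in precision depends on a correlation the documents do not give and may be near zero, particularly given section 5.3's caution about some pre-stent scores. Report the POD1-to-POD7 change as a secondary outcome.

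The cost is a wording change to the primary-analysis paragraph and the margin sentence. Both USSQ assessments are already scheduled, and on the additive scale 47 per arm gives 82% power. There are two small downsides. If the POD1-POD7 correlation is above .5, POD7 alone has a larger SD than the change. If ANCOVA is used, missing pre-stent scores need simple baseline imputation or a missing indicator.

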# **1.0 STUDY SUMMARY**

# **1.1 AIM AND HYPOTHESIS**

The objective of this project is to compare the efficacy of hyoscyamine to tamsulosin monotherapy in treating lower urinary tract symptoms in patients with indwelling double-J ureteral stents.

Ureteral stents are routinely used in a variety of urologic conditions. Unfortunately, indwelling ureteral stents commonly cause significant pain and discomfort due to irritation to the urinary system. Many studies have looked at methods to reduce these uncomfortable symptoms ranging from altering stent designs to pharmacologic therapies attempting to alleviate stent-discomfort. However, stent-related discomfort continues to be an issue and is often the cause of their removal earlier than planned. While the efficacy of certain alpha blockers and anticholinergics in treating stent-related symptoms have been studied, the data for the use of hyoscyamine in this setting is lacking. A literature search yielded no studies evaluating the use of hyoscyamine in this setting to date. We hypothesize that hyoscyamine (brand name Levsin) is equivalent to tamsulosin in treating lower urinary tract symptoms in patients with indwelling double-J ureteral stents due to its anticholinergic properties. Furthermore, we hypothesize that patients in the hyoscyamine arm will not require additional pain medications (e.g. Pyridium, narcotics) to help control stent-related discomfort compared to the tamsulosin arm.

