# 4.2 EXCLUSION CRITERIA

- 1. Patients younger than 18 years of age
- 2. Patients with chronic or pre-existing indwelling stents
- 3. Patients currently receiving anticholinergic or alpha blocker therapy
- 4. Patients with chronic opioid or analgesic usage
- 5. Patients with chronic pain syndrome or symptomatic benign prostatic hyperplasia
- 6. Patients with an active untreated urinary tract infection
- 7. Patients who are currently pregnant or nursing
- 8. Patients with allergies or contraindication to either tamsulosin or hyoscyamine
- 9. Patients on active chemotherapy
- 10. Patients currently receiving other investigational therapy
- 11. Patients who are unable to sign consent/answer questionnaire due to compromised mental capacity or language barrier (the questionnaire is not validated in other languages)
- 12. Patients who have a stent placed emergently for an obstructing stone or septic stone without immediate stone removal,

13. Any stents placed that will stay in for longer than 2 weeks, including patients who suffered a ureteral injury (Grade 2 or above) during the procedure that will be classified as a screen fail

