Questionnaires will be completed either in person if patient is in clinic or inpatient, or via a REDCap survey prior to stent placement, POD1, POD7 or at the time of stent removal if the removal occurs prior to day 7, and POD30. Patients with strings attach to stents will be included as there is no literature to suggest that strings cause additional stent irritation. Both medications will be stopped once the ureteral stent is removed as part of routine urological follow-up care for the primary etiology. Once the number of study participants reaches the pre-determined goal as calculated by our biostatistician, study enrollment will conclude and we will begin analyzing the data.

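### The primary change score spans anything from 0 to 6 days depending on when the stent comes out, and the plan neither sets a minimum nor examines the effect

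*Combined protocol and SAP*

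**What the plan says.** Section 5.5 makes the primary comparison a non-inferiority t-test, by randomised arm, on the "change in USI between POD1 and POD7 (or day of stent removal if removed before day 7) in each treatment arm". The procedures in section 5.3 place the second questionnaire at "POD7 (or just prior to the time of stent removal if the removal occurs prior to day 7"; the footnote to the schedule in section 5.6 says "If stent is removed prior to day seven then USSQ will occur on day of stent removal and diary will be stopped". Study drug ends with the stent: "Both medications will be stopped once the ureteral stent is removed".

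The only dwell limit in eligibility is an upper one. Exclusion 13 in section 4.2 rules out "Any stents placed that will stay in for longer than 2 weeks". There is no lower limit, and section 5.3 adds that "Patients with strings attach to stents will be included" with no dwell condition attached.

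The protocol expects early removal. Section 1.1 says that stent discomfort "is often the cause of their removal earlier than planned", and section 2.1 cites a study in which 32% of patients asked for premature removal. Section 5.3 lists stent duration among the data collected. No analysis in section 5.5 uses it, and the reason for removal is not listed. Nothing says what happens to the primary endpoint if the stent is out on or before POD1.

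**The concern.** A t-test on change scores treats every patient's change as the same quantity. Here one patient's change may cover six days of treatment and another's one day or none. Patients with no interval carry no information about the drugs, yet they pull the arm means together. In a non-inferiority trial, anything that pulls the arms together needs a guard, because similarity is what the trial sets out to show.

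The second risk is that the interval is an outcome. If one drug controls symptoms less well, its patients may have stents out sooner and be scored over shorter periods. The arms would then differ in what is measured as well as in how well patients do, and the direction of the bias cannot be assumed. The plan does not separate removals that were always planned early from those brought forward by symptoms.

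**Working it through.** **Inputs from the documents.** Section 5.4: 47 per arm, one-sided alpha .025, nominal power 80%, margin 15%, CV of the USI .25. Section 5.5: the endpoint.

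**Assumptions.** The SD of the change is .25 of the mean USI. As SD of change = .25 × √(2(1 − ρ)), this is a POD1–POD7 correlation of ρ = .5. A share f of each arm has exactly zero change. The documents give no value for f, so a range is shown.

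**1. The plan's own figure.** With margin .15, SD .25 and no true difference, the noncentral t gives 45 per arm for 80% power, within 2 of the stated 47. At 47 per arm, SE = .25 × √(2/47) = .0516, .15/.0516 = 2.91, and power is 82.1%.

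**2. The interval.** POD1 to POD7 is 6 days. Removal on POD k, for k = 1 to 6, leaves k − 1 days, that is 0 to 5. Only k = 1 forces a change of about zero, and only if the questionnaire precedes removal.

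**3. Dilution.** If the true difference in fully observed patients is D, the expected observed difference is (1 − f) × D. With D = .15 this is .135 at f = 10% and .120 at f = 20%.

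**4. Fixed margin (.15), true deficit at the margin.** The shift towards declaring non-inferiority is .15f/SE. At f = 10% it is .015/.0516 = .29, and the chance of a false conclusion is 4.7%. If zero-change patients also have no spread, the variance is .9 × .25² + .1 × .9 × .075² = .0568, the SD is .238, and the chance is 4.9%.

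**5. Margin scaling with the observed change, no true difference.** The margin becomes .15(1 − f). At f = 10%, .135/.0516 = 2.62 and power is 73.6%. With no spread in the zero-change patients, the SD is .25 × √.9 = .237, the SE is .0489, .135/.0489 = 2.76, and power is 77.9%.

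| f | Expected difference when D = .15 | False non-inferiority, fixed margin | Power, scaled margin |
|---|---|---|---|
| 0 | .150 | 2.5% | 82.1% |
| 5% | .1425 | 3.5% | 78.1–80.1% |
| 10% | .135 | 4.7–4.9% | 73.6–77.9% |
| 20% | .120 | 8.3–9.3% | 63.4–73.1% |
| 30% | .105 | 13.5–17.3% | 52.2–67.3% |

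Each range runs over the spread in zero-change patients, from equal to the others' to none.

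**Limits of the illustration.** It omits the extra variance from mixing zero with a non-zero mean change, because no mean change is given. That variance would soften the fixed-margin column and lower the power column. It also starts from a margin of .15 of the mean USI. A margin of 15% of the change would be smaller whenever the change is less than the whole USI, so power would be lower even at f = 0.

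**The case against.** The strongest reply is that scoring symptoms up to removal is a defensible choice in a comparative effectiveness trial, and that much of what seems to follow from it is not in the documents. Four stronger readings are tempting.

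- *Every early removal contributes roughly no change.* This is not supported. It is structural for POD1 removal only. For POD2 to POD6 the interval is shorter, but the documents give no time course. Section 5.5 itself says that information on POD1 scores is too thin to estimate the change, and much of it could come early.
- *The 32% in section 2.1 is the share affected.* It is not. It counts requests for premature removal in another study, not removals before POD7 here, and still less removals on POD1.
- *The design favours false non-inferiority.* That holds only for a fixed-point margin. Section 5.4 frames the margin as "hyoscyamine is not inferior to tamsulosin by more than a 15% margin in terms of the USI", whereas section 5.5 makes it 15% of the change, in which case the main cost is power.
- *Symptom-driven removal leaves no trace.* Stent duration is recorded. A questionnaire completed just before a stent is removed for severe symptoms can carry a high USI into the primary comparison as a poor result. What is missing is a planned analysis of duration and reason.

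On the remedy, it can fairly be said that randomisation precedes stent placement and that operative findings can alter planned dwell, as exclusion 13 acknowledges. Some misclassification is unavoidable.

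All of this limits the size and reach of the point. It does not remove the case with no interval, the unequal intervals, or the lack of any analysis that would show whether they mattered.

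**Conclusion.** The point holds in a limited form and calls for a cheap improvement. The primary change score covers 0 to 6 days, no minimum planned dwell is set, and POD1 removals with the questionnaire done first give about zero change whichever drug was assigned. These patients can dilute the arm difference. Because the protocol ties discomfort to early removal, the interval may depend on treatment, and the direction of the bias is then open.

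The size is unknown. At a 10% zero-change share the illustration gives either a doubling of the false non-inferiority rate to about 5% or a fall in power of roughly 4 to 8 points. Which one applies depends on a margin that sections 5.4 and 5.5 define differently. Both figures rest on an assumed share, an SD borrowed from the USI level, and exactly zero change in those patients. A reader should not infer that the trial is biased towards non-inferiority, or that 10% or more of stents will come out on POD1; the documents show neither.

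**What to change.** 1. Record the planned removal day before randomisation. Add to section 4.2 that patients whose stent is already planned to come out on or before POD1 are not enrolled, since the endpoint has no interval for them. The actual removal date stays with the treating urologist.
2. Prespecify a repeat of the non-inferiority test, by randomised arm, in patients whose removal was planned before randomisation for POD7 or later. This subgroup is fixed at baseline, so the randomised comparison is kept. Stratifying the REDCap randomisation on it is optional. The result is supportive, with fewer than 47 per arm if any patient is planned earlier.
3. Record whether an earlier-than-planned removal was for stent symptoms. Report that proportion and the stent dwell by arm. Prespecify a sensitivity analysis that gives those patients a stated unfavourable USI change, with the value written down before any results by arm are seen.
4. Reconcile the margin in sections 5.4 and 5.5, and make sections 5.3, 5.5 and 5.6 agree on whether the removal-day questionnaire comes before removal.

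The cost is a short addition to the case report form, one eligibility line, a little more analysis and a few patients not enrolled. Some patients will be misclassified because operative findings can change the planned dwell.
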